10. EFFICACY

Subjects will be analysed on the FAS for all items collected in the case report form (CRF.)

Secondary efficacy criteria will be described at each assessment time, as well as changes from baseline (when applicable), in accordance with the chapter §6.2.

10.1. Analysis of the primary efficacy criterion

Analysis of primary efficacy criterion (16S rRNA gene high throughput sequencing) will be described in a separate document. The analysis population will be defined according to the results of the sequencing process.

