8.1.5.3 Assessment of sino-nasal microbial communities by 16S rRNA gene amplicon sequencing

DNA extraction

Genomic DNA (gDNA) is extracted using an optimized tissue-specific technique as previously described [14], [15]. This technique was carefully designed to maximize the recovery of bacterial DNA and to minimize any risk of contamination from the environment and the reagents. The quality and quantity of extracted gDNA are monitored by gel electrophoresis (1% w/w agarose in 0.5× TBE buffer) and NanoDrop 2000 UV spectrophotometer (ThermoFisher Scientific). All gDNA samples are stored at -20 °C until further processing.

Bacterial quantification by quantitative PCR (qPCR)

Total number of bacterial 16S rRNA gene copies is evaluated by real-time PCR amplification targeting the hypervariable regions V3-V4 with the primers: EUBF 5'-TCCTACGGGAGGCAGCAGT-3' and EUBR 5'-GGACTACCAGGGTATCTAACCTGTT-3'. The qPCR is realized in triplicate on a ViiA 7 PCR system (Life Technologies) using SYBR Green technology and the specificity of all qPCR products is assessed by systematic analysis of a post-PCR dissociation curve performed between 60°C and 95°C. The absolute number of copies of the 16S rRNA gene is determined by comparison with a quantitative standard curve generated by serial dilution of linearized plasmid standards.

Bacterial 16S rRNA gene sequencing

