The V3-V4 hypervariable regions of the 16S rRNA gene are amplified by PCR using universal primer Vaiomer 1F (CTTCCCTACACGACGCTTCCGATCT-TCCTACGGGAGGCAGCAGT, partial P5 adapter-primer) and universal primer Vaiomer 1R (GGAGTTCAGACGTGTGCTTCCGATCT-GGACTACCAGGGTATCTAACCTGTT, partial P7 adapter-primer), which are fusion primers based on the qPCR primers with sequencing adapters. The first PCR reaction is carried out on a Veriti Thermal Cycler (Life Technologies) as follows: an initial denaturation step (94°C for 10 min), 35 cycles of amplification (94°C for 1 min, 68°C for 1 min and 72°C for 1 min) and a final elongation step at 72°C for 10 min. Amplicons (467 bp on the Escherichia coli reference genome) are then purified using the magnetic beads CleanNGS for DNA clean-up (CleanNA). A second PCR reaction for sample multiplexing is performed using tailor-made 6-bp unique index sequences with the forward primer Vaiomer 2F (AATGATA CGCG ACCACGAGATCTACACT-CTTCCCTACACGAC, partial P5 adapter-primer targeting primer 1F) and reverse primer Vaiomer 2R (CAAGCAGAAGACGGCATACGAGAT-index-GTGACT-GGAGTTCAGACGTGT, partial P7 adapter including index-primer targeting primer 1R). This second PCR step is run as follows: an initial denaturation step (94°C for 10 min), 12 cycles of amplification (94°C for 1 min, 65°C for 1 min and 72°C for 1 min) and a final elongation step at 72°C for 10 min. Amplicons are purified as described for the first PCR round. All libraries are pooled in the same quantity to generate an equivalent number of raw reads and are sequenced on a MiSeq Illumina platform (2 x 300 bp paired-end MiSeq kit v3, Illumina).

16S rRNA Gene Sequence Analysis

The targeted metagenomic sequences are analyzed using a bioinformatics pipeline based on 'find, rapidly, OTUs with Galaxy solution' (FROGS) guidelines [16]. In brief, after demultiplexing of barcoded Illumina paired reads, single-read sequences were cleaned and paired into longer fragments. OTUs are produced with single-linkage clustering. The taxonomic assignment is performed by BLAST against SILVA database to determine bacterial profiles from phylum to genus, and when reachable to species level. The following filters are applied: amplicons with a length of <350 nt or a length of

>490 nt are removed and OTUs with abundance lower than 0.005% and that appear less than twice in the entire dataset are removed. Alpha and beta diversity analyses are conducted on the OTU table.

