15.2 Subject privacy

This research falls within the scope of the reference methodology MR-001 relating to the processing of personal health data carried out in the context of a research involving the subject's consent collection. The sponsor has signed a commitment to comply with the provisions of MR-001 (CNIL receipt number: 2222437v0 dated from 21st May 2021).

All records identifying directly and/or indirectly the subject will be kept confidential according to the French law n°78-17 *relative to data processing, files and liberties* and the European Regulation 2016/679 effective as of 25 May 2018 (hereafter the "GDPR") and will not be made publicly available.

The present study will be conducted under Regulation 2016/679/EU of the European Parliament and of the Council of 27 April 2016 on the protection of natural persons with regard to the personal data and free movement of such data (GDPR).

In accordance with GDPR, the Sponsor is the "Controller" and the participating sites, monitors, data managers and statisticians are "Processors". Lallemand Pharma, sponsor of the study, is responsible for the processing of the study data. The Data Protection Officer appointed by Lallemand Pharma: [name], [contact].

Confidentiality of data shall be observed by all parties involved throughout the clinical investigation. All data will be secured against unauthorized access. Subject names will not be sent to the sponsor. Only the patient number will be recorded in the CRF, and if the patient's name appears on any document, it must be obliterated before a copy of the document is supplied to the sponsor. All subject data that appear in reports and publications will be anonymised such that the privacy and confidentiality of each subject is maintained.

To characterize the nasal microbiome by quantitative PCR and 16S rRNA gene sequencing, VAIOMER will receive patient biological samples identified by anonymized sample codes. To ensure that personal data cannot be attributed to specific samples, the decoding index will not be communicated to Vaiomer at any time. Moreover, to protect the integrity and the confidentiality of the data generated by Vaiomer, below are the relevant actions in place:

- **Physical location**

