4. SAMPLE SIZE

An arbitrary sample of 20 subjects completing the investigation without major protocol deviation has been chosen.

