5. DEFINITION OF THE ANALYSIS SETS

Screened subjects: all subjects who signed an informed consent

Included subjects: all screened subjects who will have been expected to participate in the study.

Safety Set: all subjects who will have used the investigational medical device at least once.

Full Analysis Set (FAS): all subjects from the Safety Set who will have at least one post baseline Sino Nasal Outcome Test-22 (SNOT-22) evaluation.

Per Protocol Set (PP): all subjects from the FAS without any major protocol deviation.

The status of protocol deviations (minor or major) will be validated during the data review meeting.

Any subject not satisfying major entry criteria or for whom post inclusion data are not available will be identified by the Validation Committee during the data review, and could be excluded from the FAS Set in agreement with circumstances exposed in the ICH-E9 §5.2.1.

Safety analysis will be performed on the Safety Set.

Efficacy analysis (except primary efficacy criterion) will be performed on the FAS.

Note: primary efficacy criterion (16S rRNA gene high throughput sequencing) will be analysed separately by a dedicated team specialized in microbiome analysis.

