6.3. Statistical/Analytical issues

6.3.1. Significance level

All statistical analyses will be performed at the 0.05 global significance level (type I error rate), using two-sided tests.

Because of the exploratory nature of the study, all the statistical results have to be considered within a descriptive perspective and not as inferential issues. No adjustment for Type I error is done. P-values of statistical tests will be provided for information only.

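### Does letting the sequencing results define the primary-analysis population leave room for outcome-dependent exclusion?

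*SAP*

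**What the plan says.** SAP section 5 defines the Safety Set, FAS and PP set, then sets the primary criterion apart: "Efficacy analysis (except primary efficacy criterion) will be performed on the FAS". A note there gives the primary criterion to a specialised microbiome team. SAP 10.1 adds two sentences: "Analysis of primary efficacy criterion (16S rRNA gene high throughput sequencing) will be described in a separate document" and "The analysis population will be defined according to the results of the sequencing process". In both sections the criterion is described by 16S sequencing alone. Protocol 8.1.3 is wider and also puts bacterial load by qPCR in the primary endpoint.

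Protocol 8.1.5.3 describes the laboratory work. Its numerical filters act on amplicon length and on OTU abundance, not on whole samples. Among the major deviations in Protocol 13 and SAP 7.2, the only swab-related item is a swab that was not collected.

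Four other statements bear on the point. Protocol 11.6 uses the pre-lock data review to define the analysis populations, and requires each subject's evaluability to be decided and documented before lock. Protocol 15.2 says of the laboratory that "the decoding index will not be communicated to Vaiomer at any time". SAP 6.3.1 says "P-values of statistical tests will be provided for information only". SAP 4 gives the size: "An arbitrary sample of 20 subjects completing the investigation without major protocol deviation has been chosen".

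**The concern.** A population that depends on results is normally a warning sign. If the same data that carry the endpoint also decide who is counted, exclusions can follow the outcome. Here there is a plausible route: a swab holding little bacterial DNA may be more likely to fail sequencing. If treatment lowers load, more V2 swabs than V1 swabs would fail, the remaining patients would be those whose load fell least, and the fall would be understated. The bias for diversity and taxa could go either way.

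Three things are not stated in the protocol or SAP: a sample-level failure rule, a point at which the separate document is final relative to the results, and a population for qPCR load. Subjects are not replaced (Protocol 8.1.7), so each lost pair is 1/20 = 5% of the planned sample.

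**Working it through.** The plan gives no figure to reproduce: the 20 is declared arbitrary and has no effect size, SD or power behind it. The check is therefore a reading of the text, followed by an illustration of size on assumed inputs.

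**Reading.** SAP 5 and 10.1 tie the population to the sequencing process and name only 16S sequencing. The ordinary reading is that a swab without usable sequence cannot contribute diversity or taxa. Nothing in either section carries that population over to qPCR, a separate triplicate assay in Protocol 8.1.5.3. Two laboratory features weaken the link between load and failure: "All libraries are pooled in the same quantity to generate an equivalent number of raw reads", and, of the DNA extraction, "This technique was carefully designed to maximize the recovery of bacterial DNA".

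**How many pairs might go.** With an assumed independent failure rate f per swab, expected complete pairs = 20(1-f)^2 and the chance of losing none = (1-f)^40. At f = 5% these are 18.05 and 0.13; at f = 10%, 16.2 and 0.015. The standardised paired change detectable with 80% power (two-sided 0.05) moves from 0.66 at 20 pairs to 0.70 at 18 and 0.75 at 16.

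**Load, if the sequencing population were applied to it.** Assumptions: log10 copies bivariate normal, V1 mean 5, true change -0.50, SD 0.8, within-patient correlation rho 0.3 to 0.7. A swab fails below the 1st, 5th or 10th percentile of baseline load, and incomplete pairs are dropped. The 20-pair standard error is sqrt(2 x 0.8^2 x (1-rho)/20) = 0.212, 0.179 and 0.139 for rho 0.3, 0.5 and 0.7. Simulated estimates under a hard cut-off, with bias/SE in brackets:

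| rho | 1st | 5th | 10th |
|---|---|---|---|
| 0.3 | -0.459 (0.19) | -0.400 (0.47) | -0.359 (0.67) |
| 0.5 | -0.470 (0.17) | -0.425 (0.42) | -0.392 (0.60) |
| 0.7 | -0.481 (0.13) | -0.451 (0.35) | -0.428 (0.52) |

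About 19 to 14 pairs remain. If load and sequencing yield correlate only 0.5, the estimates run from -0.497 to -0.470 (at most 0.03/0.212 = 0.14 SE). If failure is unrelated to load, or there is no true change, the bias is zero.

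These are not bounds. At SD 0.5 the bias exceeds one standard error in two of nine cells (1.10 and 1.21). Protocol 9 names rank-sum-type tests and no rule that drops incomplete pairs. If every usable swab is kept, each visit mean above the cut-off c is mu + SD x phi(k)/(1-Phi(k)), with k = (c-mu)/SD. At the 5th percentile (c = 3.684) V1 is 5.087 and V2 is 4.724, a change of -0.36. At the 10th (c = 3.975) they are 5.156 and 4.846, a change of -0.31. The latter bias, 0.19, is 0.19/0.139 = 1.37 of the smallest standard error above. The answer follows the assumptions, none of which come from the documents.

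**Diversity, which the sentence does cover.** Assume a true Shannon change of +0.30 with SD 0.6, so SE = 0.6/sqrt(20) = 0.13, and correlation with load change from -0.5 to +0.5. The hard cut-off gives 0.255 to 0.344, a shift of at most 0.045/0.134 = 0.34 SE in either direction. The weaker link gives 0.290 to 0.309.

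**What an explicit load rule would gain.** Suppose load were analysed in every patient with two valid qPCR results, with values below the quantification limit set to that limit. If the limit equals the load at which sequencing fails, the estimates are -0.488, -0.452 and -0.415 at the three percentiles. Against the table, seven cells improve by 0.007 to 0.056, one by 0.001 and one worsens by 0.013. Under the weaker link, with the same limit applied to the sequenced pairs, the gain is at most 0.006 and the loss up to 0.019. A clear gain needs a limit well below the failure load: limit at the 1st percentile and failure at the 5th or 10th gives -0.488 against -0.45 to -0.36.

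**The case for a change.** The best case for a change rests on documentation. The primary criterion is the only efficacy criterion for which the SAP defines no population. Protocol 11.6 does not mention the sequencing data, and it does not say that lock comes before anyone sees them. SAP 12 reports a change made after data review, so this version postdates that review, yet 10.1 still speaks of the population in the future tense. Withholding the decoding index is a privacy measure; nothing says the sample codes hide the visit. In the hard cut-off example, V1 failure rates of 1%, 5% and 10% become about 4%, 15% and 26% at V2, and only a table of failures by visit would show it. The results are also meant to inform whether larger studies follow.

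These observations are correct as far as the two documents go. They establish that detail is delegated, not that it is absent: the separate document is the natural home for a failure rule, its timing and the load population. They do not show that any exclusion followed the outcome. SAP 13.2 already plans a listing of subjects excluded from the efficacy analysis (Listing 16.2.3), although it is not said to cover sequencing failures. A cross-reference to the separate document's version and date would be tidy, but would alter no analysis.

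**Conclusion.** The concern does not call for a change. The factual core is right: the protocol and SAP give no sample-level failure rule, no finalisation point for the separate document and no population for qPCR load. But this is detail left to the microbiome team and to a document outside this review, and the sentence in SAP 10.1 most naturally describes technical success. The pre-lock step in Protocol 11.6 covers populations and evaluability in general terms.

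For the outcomes the sentence governs, the illustrated shift is at most about a third of a standard error and has no known direction. The larger load figures need a reading the SAP does not make, a failure threshold driven by load and a true fall in load. A more explicit load rule would not dependably improve the estimate. In an exploratory single-arm study of 20 patients read descriptively, that does not justify amending the plan. This conclusion assumes that the microbiome team excludes swabs on technical grounds only and reports how many were lost. If exclusions were instead made with knowledge of visit and outcome, it would not hold, but nothing in the documents indicates that.

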10.2. Analysis of the secondary efficacy criteria

Each item of the SNOT-22, the nasal, ear/facial, sleep, function and emotion sub-domains (refer to §8.4 for definition) and the resulting overall score and change from baseline will be described at end of study.

Subject satisfaction (questions on 4-point Likert scale) will be described at end of study.
Symptoms of chronic rhino sinusitis and change from baseline will be described at end of study.

11. SAFETY

The following parameters will be analysed on the Safety Set.

11.1. Study duration

Study duration will be calculated according to the formulas below:

Study duration (days) = Reference End Date – Reference Start Date + 1

11.2. Adverse events

Note: in the following paragraph, for a smoother reading:

- Incidents and adverse events will be referred as adverse events (AE);
- treatment-emergent incidents and adverse events will be referred as treatment-emergent adverse event (TEAE).

AE are coded using the MedDRA dictionary version 25.0. They are classified by System Organ Class and Preferred Term.

An AE will be considered as a TEAE if:

- it was not present prior to the reference start date
- it was present prior to the reference start date and worsened during the study (increase of intensity)
- it reappears after the reference start date (finished before the reference end date)

A given TEAE (according to the MedDRA terminology) will be counted only once per subject. If a subject experienced several AEs in the same SOC/PT, the most severe intensity will be retained for this SOC/PT.

Note: if the intensity/severity is missing, a conservative approach will be adopted and the intensity/severity will be considered as severe.

Missing or incomplete dates will be estimated as described in section §6.4.4 in order to determine the TEAEs, but they will be presented as reported in CRF in the data listings. Generally, an AE for which the onset date is missing or incomplete and does not permit to identify the onset according to the date of the reference start date (i.e. missing onset day and month/year corresponding to the reference start date) will be considered as treatment-emergent.

Tables will present separately:

- **incidents related to the use of the medical device** (described as possibly related, probably related or related with the device in the eCRF),
- **adverse events not related to the use of the medical device**

- Summary of adverse-events

Summary tables will be produced for AEs not related to the use of medical device and for incidents related to the use of the medical device. Tables will be adapted depending on the definition of the type of AE

- number and percentage of subjects with at least one adverse event (AE)
- number and percentage of subjects with at least one AE leading to definitive study device discontinuation
- number and percentage of subjects with at least one AE leading to definitive study discontinuation
- number and percentage of subjects with at least one serious adverse event (SAE)
- number and percentage of subjects with at least one TEAE
 - number and percentage of subjects with one TEAE
 - number and percentage of subjects with two TEAE
 - number and percentage of subjects with at least three TEAE

- Analysis of treatment-emergent adverse event

Only TEAE will be summarised by System Organ Class and Preferred term. The following tables will be provided:

- number and percentage of subjects with TEAE for AEs related to the chronic rhino sinusitis,
- number and percentage of subjects with TEAE for AEs related to the sino-nasal swab procedure,
- number and percentage of subjects with TEAE for incidents related to the use of the medical device

- Analysis of deaths, other serious adverse events and other significant adverse events

A listing of deaths will be provided if applicable.

A listing of serious adverse events will be also provided if applicable.

All AEs leading to definitive discontinuation of the trial device or definitive discontinuation of the trial will be listed if applicable.

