16.1 Definitions

Incident means any malfunction or deterioration in the characteristics or performance of a device made available on the market, including use-error due to ergonomic features, as well as any inadequacy in the information supplied by the manufacturer and any undesirable side-effect (MDR 2017/745, article 2 (64)).

Serious incident means any incident that directly or indirectly led, might have led or might lead to any of the following: (a) the death of a patient, user or other person, (b) the temporary or permanent serious deterioration of a patient's, user's or other person's state of health, (c) a serious public health threat (MDR 2017/745, article 2(65)).

Serious public health threat means an event which could result in imminent risk of death, serious deterioration in a person's state of health, or serious illness, that may require prompt remedial action, and that may cause significant morbidity or mortality in humans, or that is unusual or unexpected for the given place and time (MDR 2017/745, article 2(66)).

Expected and foreseeable side effects (MEDDEV 2 12-1 rev. 8)

They meet all the following criteria:

- Clearly identified in the manufacturer's labelling;
- Clinically well known as being foreseeable and having a certain qualitative and quantitative predictability when the device is used and performs as intended;
- Documented in the device master record, with an appropriate risk assessment, prior to the occurrence of the incident and
- Clinically acceptable in terms of the individual patient benefit.

Adverse event means any untoward medical occurrence, unintended disease or injury or any untoward clinical signs, including an abnormal laboratory finding, in subjects, users or other persons, in the context of a clinical investigation, whether related or not related to the investigational device (MDR 2017/745, article 2(57)).

Adverse or intercurrent events are graded as follows:

- Mild: Awareness of signs or symptoms but easily tolerated.
- Moderate: Uncomfortable enough to cause interference with usual activity.
- Severe: Incapacity with inability to work or do usual activity.

Serious Adverse Event means any adverse event that led to any of the following:

- (a) death,
- (b) serious deterioration in the health of the subject, that resulted in any of the following:
 - (i) life-threatening illness or injury,
 - (ii) permanent impairment of a body structure or a body function,

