Table	14.3.2.5	Safety – Serious TEAE (incidents) related to the use of the medical device by System Organ Class and preferred term [Safety Set]
Table	14.3.2.6	Safety – Serious TEAE not related to the use of the medical device by System Organ Class and preferred term [Safety Set]

SUBJECTS DATA LISTINGS

[figure not shown]
Listing	16.2.1	Discontinued subjects
Listing	16.2.2	Protocol deviations
Listing	16.2.3	Subjects excluded from the efficacy analysis
Listing	16.2.4	Demographic data
Listing	16.2.5	Compliance data
Listing	16.2.6	Individual efficacy response data

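### Tables 14.3.2.3 and 14.3.2.5 can count device faults without harm as treatment-emergent adverse events, and the rule for 'serious' is ambiguous

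*SAP*

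**What the plan says.** SAP 11.2 opens its adverse event rules with a convention, introduced by "Note: in the following paragraph, for a smoother reading". It has two parts: "Incidents and adverse events will be referred as adverse events (AE", and "treatment-emergent incidents and adverse events will be referred as treatment-emergent adverse event (TEAE". The section then applies one MedDRA coding, one treatment-emergence rule and one missing-intensity rule to the combined category. It separates the output only by relation to the device.

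In SAP 13.2, Table 14.3.2.3 covers device-related TEAE (incidents), and the title of Table 14.3.2.5 begins "Serious TEAE (incidents) related to the use of the medical device by System Organ Class and preferred term". Both mock tables have one 'All' row, followed by system organ class and preferred term.

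Protocol 16.1 gives separate definitions. For incidents: "Incident means any malfunction or deterioration in the characteristics or performance of a device made available on the market". The sentence goes on to add use error, inadequate manufacturer information and undesirable side effects. For adverse events: "Adverse event means any untoward medical occurrence, unintended disease or injury or any untoward clinical signs". The two seriousness rules are "Serious incident means any incident that directly or indirectly led, might have led or might lead to any of the following" and "Serious Adverse Event means any adverse event that led to any of the following".

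Protocol 16.2 sends incidents and risks of incidents to the CRF, alongside adverse events and expected side effects. Protocol section 9 plans a summary of treatment-emergent adverse events/incidents and of expected side effects by system organ class and preferred term.

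**The concern.** The safety objective is systemic and local tolerance, and the only anticipated device effect is itching and irritation at the start of treatment (Protocol 6.2). A reader will take the 'All' row of the device-related TEAE table as the share of patients who had a side effect. If that row can also hold a leaking can or a blocked actuator with no symptom, it no longer measures tolerance. If a fault with only potential harm can enter the serious table, a reported serious TEAE need not mean that anyone was harmed. No planned row isolates the expected side effects that Protocol section 9 says will be summarised.

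**Working it through.** There is no figure in the plan to reproduce: the point concerns definitions and table content, and the sample of 20 is described as arbitrary (SAP 4).

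**1. Definitions side by side (Protocol 16.1)**

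| | Needs a medical occurrence in a person? | Serious when |
|---|---|---|
| Incident | No: a malfunction, use error or inadequate information is enough | it led, or could have led or could lead, to a listed outcome |
| Adverse event | Yes | it led to a listed outcome |

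The incident category therefore contains events that are not adverse events, and its seriousness threshold is lower.

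**2. Path of a fault without symptoms under the SAP**

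- A can leaks during the study and the patient has no symptom. Under Protocol 16.1 this is an incident and not an adverse event.
- Protocol 16.2 has it recorded in the CRF.
- It was not present before the reference start date, so it meets the treatment-emergence rule in SAP 11.2.
- If its relation to the device is recorded as possible, probable or related, it goes into the device-related tables.
- It is counted in the 'All' row of Table 14.3.2.3.

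**3. Seriousness**

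The summary item in SAP 11.2 is worded as a serious adverse event (SAE). The corresponding mock row of Table 14.3.2.1 reads 'Serious incident'. The title of Table 14.3.2.5 uses both terms. By the SAE definition, a fault with only potential for serious harm is not counted. By the serious incident definition, it is. The SAP does not say which rule Table 14.3.2.5 uses, so two programmers could produce different counts.

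**4. Size (illustrative, Safety Set assumed to be N = 20)**

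- One subject whose only related event is a fault without harm adds 100/N = 100/20 = 5.0 percentage points.
- One such subject and no true side effect: the table shows 1/20 = 5.0% (exact 95% CI 0.1% to 24.9%). The figure for actual side effects is 0/20 = 0% (0% to 16.8%). The SAP plans no such intervals; they are given for scale.
- Assumed mix of two subjects with irritation and two others with a faulty can: the table shows 4/20 = 20%, against 2/20 = 10% with a side effect.
- The documents give no fault rate. The chance of at least one such subject is 1 − (1 − p)^20 for an assumed per-subject risk p:

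| p | Chance of at least one in 20 |
|---|---|
| 1% | 18.2% |
| 2% | 33.2% |
| 5% | 64.2% |
| 10% | 87.8% |

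**The case against.** The strongest reply is that the convention is shorthand for one section, offered as a reading aid, and changes nothing in Protocol 16.1. Several parts of this stand:

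- Device-related incidents are tabulated apart from events not related to the device (SAP 11.2 and 12). A reader might infer that faults are pooled with all adverse events; they are not.
- Table 14.3.2.1 is titled and labelled as incidents throughout, so its totals are correct for what they claim to be.
- Protocol section 9 already groups adverse events and incidents in one summary, so the grouping is not the SAP's invention. The protocol does keep the two terms distinct.
- The mock header 'Related treatment-emergent adverse events' also appears in the tables for unrelated events, and Table 14.3.2.2, for unrelated events, has rows labelled 'Incident'. This is copied template text and does not show a decision to treat faults as adverse events.
- Preferred-term rows may show a fault on its own line, and with about 20 subjects a careful reader could find it.
- The CRF page is not in the documents, so how a fault without symptoms would be graded for causality is unknown.

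The reading-aid argument does not remove the problem. The merged category also sets the treatment-emergence rule and what the tables contain, and the 'All' rows still combine faults with side effects. The SAP's statement that tables will be adapted to the type of event names no split by harm, and the mock tables show none.

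Two stronger inferences are tempting. One is that a near miss will be reported as a serious TEAE. The SAP never says so; this is one of two readings, and the SAE wording in 11.2 points the other way. The other is that an ungraded fault would be reported as severe under the missing-intensity rule. The rule would apply, but no planned table reports intensity.

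**Conclusion.** The point holds as a flaw in the counting rule. As written, a device-related fault with no medical occurrence counts as a related TEAE in Table 14.3.2.3, against the protocol's own definition of an adverse event, and the seriousness rule for Table 14.3.2.5 is undetermined. Each affected subject would add 5 percentage points to the 'All' row if the Safety Set is 20. That size rests on two assumptions: that a fault without harm occurs, and that it is recorded as device-related. The documents establish neither, so a reader should not infer that the reported safety results are wrong. The primary endpoint and the other efficacy results are untouched. The change is still worth making, because these tables are meant to answer the tolerance objective.

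**What to change.** Keep the incident totals in Table 14.3.2.1 for vigilance. In Tables 14.3.2.3 and 14.3.2.5:

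- report as TEAE only incidents with a medical occurrence in the patient, including the expected side effects;
- show malfunction, use error or inadequate information without such an occurrence in a separate row;
- apply the Protocol 16.1 SAE definition to serious TEAEs;
- show serious incidents with potential harm only in their own row.

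State the seriousness rule once in SAP 11.2, and use the same term in the text, the table titles and the mock rows.

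The cost is some SAP wording, a few extra rows and smaller counts per row. The few incidents must also be classified from the CRF or the notification form at data review. The form has fields for seriousness criteria and a narrative (Protocol Appendix E), but the documents do not show that these reach the analysis database, so a short reconciliation with vigilance may be needed. SAP section 12 shows that a data review has already been held, so the classification should be documented as an addition to it.
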